4.2 Statistical and Analytical Methods

4.2.1 Analysis Populations and Analysis Groups

Population of Patients Enrolled [EP]

The population of patients enrolled comprises all patients who voluntarily sign and date an informed consent prior to inclusion into the study and data were captured in the eCRF.

Target Population [TP]

Patients will be included if the following applies:

- Age at least 18 years
- Confirmed CHC with genotype 1 and/or 4 only, receiving combination therapy with the interferon-free ABBVIE REGIMEN \pm RBV. The prescribed ABBVIE REGIMEN needs to be known.
- Have voluntarily signed and dated an informed consent prior to inclusion into the study
- Must not be participating or intending to participate in a concurrent interventional therapeutic trial

Core Population [CP]

The core population is defined as all patients of the target population (TP) (definition see above), who are adequately treated according to the standard of care and within local label recommendations for their specific disease characteristics (cirrhotic status, genotype). The following patients will be excluded from the CP:

- Patients with unknown fibrosis status
- Cirrhotic patients with genotype 1a not receiving ribavirin
- Patients with genotype 1 for whom 2DAA instead of 3DAA is prescribed
- Patients with genotype 4 not receiving RBV

Non-Core Population [NCP]

Patients in the TP who are not in the CP.

Core Population with Sufficient Follow-up [CPSFU {12, 24}]

In addition, the core population with sufficient follow-up data regarding SVR12 or SVR24, respectively, is defined as all CP patients,

- who have evaluable HCV RNA data ≥ 70 days or >126 days, respectively, after the last actual dose of the ABBVIE REGIMEN
- or a HCV RNA value ≥ 50 IU/mL at the last measurement
- or had HCV RNA <50 IU/mL at the last measurement, but no HCV RNA measurement ≥ 70 days or >126 days, respectively, after the last actual dose of the ABBVIE REGIMEN due to reasons related to safety (e.g. dropped out due to adverse event) or virologic failure (e.g. virologic failure such as relapse is reported in the electronic case report form (eCRF) but date and value of the corresponding HCV RNA test is missing).

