This means only patients who had virological response at their last on-treatment or post-treatment measurement, but had no HCV RNA measurements ≥ 70 days or >126 days, respectively, post-treatment for reasons not related to safety or effectiveness (e.g. lost-to-follow-up or patient not willing to perform an additional HCV RNA test ≥ 70 days or >126 days, respectively, post-treatment) will be excluded from this analysis.

Safety population [SP]

The safety population is defined as all enrolled patients who received at least one dose of the ABBVIE REGIMEN. The prescribed ABBVIE REGIMEN needs to be known.

EP and TP analysis groups

The EP/TP analysis groups are defined according to the patient's fibrosis status and genotype/subtype and standard summaries are structured as follows:

- Total (regardless of cirrhosis status)
 - (1) Total (regardless of genotype)
 - (2) G1 (Total)
 - (3) G1a (including mixed G1 subtypes and patients with G1 unknown subtype)
 - (4) G1b
 - (5) G4 (non-G1)
 - (6) Other/unknown genotype (*only for EP*)
- Patients with cirrhosis
 - (7) Total (regardless of genotype)
 - (8) G1 (Total)
 - (9) G1a (including mixed G1 subtypes and patients with unknown G1 subtype)
 - (10) G1b
 - (11) G4 (non-G1)
 - (12) Other/unknown genotype (*only for EP*)
- Patients without cirrhosis
 - (13) Total (regardless of genotype)
 - (14) G1 (Total)
 - (15) G1a (including mixed G1 subtypes and patients with unknown G1 subtype)
 - (16) G1b
 - (17) G4 (non-G1)
 - (18) Other/unknown genotype (*only for EP*)
- Patients with unknown fibrosis status
 - (19) Total (regardless of genotype)
 - (20) G1 (Total)
 - (21) G1a (including mixed subtypes and patients with unknown subtype)
 - (22) G1b
 - (23) G4 (non-G1)
 - (24) Other/unknown genotype (*only for EP*)

(HCV genotypes will be combined as follows: G1 [total], G1a*, G1b, G4 [non-G1]. * includes mixed or other G1 subtypes and patients with unknown G1 subtypes.

Most recent stage of liver fibrosis will be categorized as follows: No cirrhosis/Transition to cirrhosis, Cirrhosis. Only one method should be selected by the physicians to report stage of fibrosis. Nevertheless, if there are multiple answers the following priority will be used:

1. Biopsy,
2. Non-invasive,
3. Clinical/best guess.

For biopsy as assessment method the respective categories are defined as follows:

- “No cirrhosis” is defined by “No fibrosis”, “Mild/minimal fibrosis”, “Moderate fibrosis”

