4.2.2 Definition of Baseline and Visit Time Windows

This observational study covers three documentation periods, see Figure 1. An overview of data to be collected throughout the study is summarized in Table 2.

Table 2 - Data Documentation Schedule

Assessment/ Procedure (only available data to be collected; no diagnostic or monitoring procedures to be applied to the patients apart from those of routine clinical practice)	Baseline	Treatment Period			Post-treatment (PT) Period		
		On-treatment visits	Mid treatment visit for pts receiving 24 weeks of therapy	EoT ^b	Early PT visit	SVR 12 visit	SVR 24 visit
Informed Consent	X ^a						
Demographic information	X						
IL28B	X						
Relevant CHC disease characteristics	X						
Liver fibrosis stage	X						
CHC treatment history	X						
HCV genotype and subtype	X						
HCV RNA samples	X	X	X	X	X	X	X
Clinical chemistry and hematology	X	X	X	X	X	X	X
ABBVIE REGIMEN initiation documentation	X						
ABBVIE REGIMEN adherence		X	X	X			
Concomitant medication	X	X	X	X			
Relevant medical history, co-morbidities	X						
sAE, AE and pregnancy reporting	X	X	X	X	X ^c	X ^d	X ^d
For patients receiving RBV: Evidence, in accordance with local label, that female patient or female partner of male patient is not pregnant	X						
Viral resistance sample	X			X		X	X
Patient questionnaires – PAM-13, BMQ 18-item	X			X			
PSP evaluation		X	X	X	X	X	

Abbreviations: EoT = End of Treatment (at Week 12 or 24 or at premature discontinuation),
PT = Post-Treatment

a Written informed consent must be obtained before any data documentation in the eCRF

b Patients who prematurely discontinue should return to the site to document EoT data

c Tolerability documentation until PT week 4

d Pregnancy reporting for patients treated with DAA plus RBV

In accordance with the non-interventional nature of the study all HCV RNA measurements will be performed at the sole discretion of the physician and all HCV RNA measurements have to be entered into the eCRF. All recorded HCV RNA values will be assigned to appropriate time points (baseline, on-treatment visits, EoT visit, post-treatment visits) as follows:

Table 3 - Analysis Time Windows for HCV RNA

Phase	Time point	Time Window
Pre-Treatment	Baseline	Last value prior to start of study treatment (i.e. \leq study day 1)
On-treatment		Study day during treatment period ^{^#} (Study day 1 = first treatment day)
Treatment Week	4 (RVR*)	15 - 42 [^]

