4.2.3 Handling of missing data

No data will be imputed for any effectiveness or safety analyses except for the analyses of the HCV RNA endpoints and certain PRO endpoints. The discussion of missing data imputation for the PRO endpoints is included in section 4.2.7.2.3.

HCV RNA values will be selected for an RVR, EOTR and SVR analysis based on visit windows as defined in Table 3. When there is no HCV RNA value in a visit window based on defined visit windows, the closest values before and after the window, regardless of the value chosen for the subsequent and preceding window, will be used for the flanking imputation described below. For analysis of RVR, EOT and SVR, if a subject has a missing HCV RNA value at a post-Day 1 visit but with undetectable or unquantifiable (\leq 50 IU/mL) HCV RNA levels at both the preceding value and succeeding value, the HCV RNA level will be considered undetectable or unquantifiable, respectively, at this visit for this subject. In addition, if a subject has an unquantifiable HCV RNA level at the preceding value and an undetectable HCV RNA level at the succeeding value, or vice versa, the HCV RNA level will be imputed as unquantifiable at this visit for this subject.

For analyses of RVR, subjects still missing a value for the visit after flanking imputation will be imputed as a failure. For EoTR and SVR analysis, if there is no value in the appropriate window after flanking imputation but there is an HCV RNA value after the window, then it will be imputed into the EoTR or SVR window respectively. Subsequent to this flanking imputation, if a subject is missing a value for the visit window associated with the analysis, the subject will be imputed as a visit failure (i.e., not undetectable or unquantifiable).

If a subject starts another treatment for HCV, then all HCV RNA values for this subject measured on or after the start date of the new HCV treatment will be excluded from analyses. The subject will be considered a failure for summaries of viral response at all time points after the start of the new HCV treatment.

Due to the non-interventional nature of this study several different methods for determination of the HCV RNA value can be applied. For the purpose of the statistical analysis, a HCV RNA measurement is considered ≤ 50 IU/mL,

- if a PCR test was used

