4.2.5 Patient Disposition

The frequencies of patients belonging to the different populations (i.e. EP, TP, CP, CPSFU; SP) will be summarized by genotype and cirrhosis status and overall using the EP analysis groups as specified in section 4.2.1. The reasons for exclusion from a particular population will be also summarized in the frequency tables. Additionally, information on patient disposition will be listed.

Furthermore the frequency of patients not completing the study as defined per protocol (i.e. no HCV RNA assessment performed at least 10 weeks post-treatment), will be summarized by treatment regimen and cirrhosis status and additionally by genotype and cirrhosis status and overall for the SP and CP. The reasons for not completing the study as entered on the CRF will be displayed (i.e. failure to return, insufficient virological response (HCV RNA detectable at End of treatment, Relapse post-treatment), patient never started treatment, withdrawn consent, death, other).

Additionally, the main reason for early termination of the ABBVIE regimen (AE or SAE [Physician decision], virological non-response [Physician decision], rebound or breakthrough [Physician decision], resistance to DAA [Physician decision], patient refused to continue treatment, patient withdrew consent to participate in the study, lost to follow-up, other, unknown [if actual duration is shortened for more than 7 days]) and Ribavirin (Anemia, Nausea/Vomiting, Rash, Other) will be summarized by treatment regimen and cirrhosis status and additionally by genotype and cirrhosis status and overall for the following different analysis populations: CP and SP.

Finally the study regimens assigned at baseline will be summarized (a) by genotype and cirrhosis status and (b) by genotype and pre-treatment status (treatment naïve vs treatment experienced) for CP and SP.

An overview of Tables is given in Table 6.

Table 6 Overview of Outputs for Patient Disposition

Output Title	Output Short Name	Analysis Population
Patient Disposition by Genotype and Cirrhosis Status – EP - <country>	tdis_<c>_gc_ep	Patients Enrolled
Listing of Patient Disposition - EP- <country>	ldis_<c>_ep	Patients Enrolled
Premature Termination of the Study and its Main Reason by <Treatment Regimen/ Genotype> and Cirrhosis Status - CP - <country>	tps_<c>_<t/g>c_cp	Core population

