4.2.7.2 Secondary Variables

4.2.7.2.1 Secondary Effectiveness Variables

Response

For the other response rates (i.e. SVR24, EoT response rate, relapse rate), the simple percentage of patients and a two-sided 95% confidence interval (CI) of the percentage will be computed (based on the Wilson's score method) as well. The EoT response rate will be reported for CP and the SVR24 rate will be reported for the respective CPSFU, stratified by genotype and cirrhosis status and overall. The relapse rates will be estimated stratified by SVR window (i.e. during SVR12 window=relapse₁₂, during SVR24 window=relapse₂₄) and stratified by genotype

and cirrhosis status and overall in patients of the CP with EoT response who fulfilled the following criteria:

- completed treatment as defined previously,
- had at least one HCV RNA measurement ≥ 70 days post-treatment or was a treatment failure between EoT and 70 days post-treatment.

Viral breakthrough rates [defined as at least one documented HCV RNA <50 IU/mL followed by HCV RNA ≥ 50 IU/mL during treatment] will be estimated overall and stratified by genotype and cirrhosis status in all patients of the CP, who have at least one undetectable or unquantifiable, on-treatment HCV RNA measurement and at least one on-treatment or EoT measurement thereafter.

Non-Response

In another table, the numbers and the percentages of the SVR12 non-responder categories and responder will be summarized for CP patients, overall and stratified by genotype and cirrhosis status. The following SVR12 non-response categories will be considered:

- On-treatment virologic failure (breakthrough [defined as at least one documented HCV RNA <50 IU/mL followed by HCV RNA ≥ 50 IU/mL during treatment] or failure to suppress [each measured on-treatment HCV RNA value ≥ 50 IU/mL])
- Relapse (defined as HCV RNA <50 IU/mL at EoT or at the last on-treatment HCV RNA measurement followed by HCV RNA ≥ 50 IU/mL post-treatment and completed treatment as defined previously)
- Death and none of the above
- Premature study drug discontinuation with no on-treatment virologic failure and none of the above
- Insufficient virological response, other than those mentioned above (patients for whom insufficient virological response was reported, or who had HCV RNA ≥ 50 IU/mL post EoT and no HCV RNA test on treatment) and none of the above
- Missing SVR12 data and/or none of the above criteria

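### Relapse24 counts patients never tested after day 126 as free of relapse, and SVR24 is reported in a population whose entry depends on outcome

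*SAP*

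**What the plan says.** **Relapse.** SAP 4.2.7.2.1 reports relapse separately for the SVR12 window (relapse12) and the SVR24 window (relapse24). Table 3 sets these at days 70–126 and 127–210 after the last dose. One denominator serves both: CP patients with EoT response who completed treatment and who either have an HCV RNA result from day 70 onwards or failed between EoT and day 70. A result after day 126 is not required for relapse24.

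**SVR24.** The same section says that "the SVR24 rate will be reported for the respective CPSFU"; SVR24 is not planned in the whole CP. SAP 4.2.1 defines the core population with sufficient follow-up "regarding SVR12 or SVR24, respectively, is defined as all CP patients" who meet one of three conditions. For SVR24 these are:

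- (i) an HCV RNA value after day 126;
- (ii) a last value of 50 IU/mL or more, whenever it was taken;
- (iii) a last value below 50 IU/mL with no test after day 126 "due to reasons related to safety (e.g. dropped out due to adverse event) or virologic failure".

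The section then spells out who is left out: patients whose last value showed response and who lack a late test "for reasons not related to safety or effectiveness (e.g. lost-to-follow-up or patient not willing to perform an additional HCV RNA test". In SAP 4.2.2, "all HCV RNA measurements will be performed at the sole discretion of the physician".

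**The concern.** In a routine-practice study some patients with a good week-12 result will probably not be tested again. The plan treats them in two different ways.

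- For relapse24 they stay in the denominator, where they can only count as free of relapse. Patients who already failed before day 127 also stay, although they are no longer at risk of a first relapse.
- For SVR24 they are removed, while failures remain without needing a late test.

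So the SVR24 rate can sit below the SVR12 rate of the matching follow-up population with no late relapse at all, while first relapses after day 126 are understated. Table 8 places the virological response rates for CP and CPSFU under one output title, which invites a side-by-side reading. The shift is also larger where failures are more common, so it can widen the gaps between the planned genotype and cirrhosis strata. What is at stake is the reading of two secondary descriptive endpoints.

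**Working it through.** **The plan's own figures.** Neither document gives a figure for SVR24 or relapse24. The planning rates used below (90% and 95%) come from SAP 3.2. Its Clopper-Pearson limits reproduce: 86.71–92.71 for 417 patients at 90%, and 91.41–97.40 and 92.08–97.08 for 238 and 334 patients at 95%. Inflating for 5% non-evaluable gives 417/0.95 = 439, against the stated 440.

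**Relapse24.** Assumed inputs, not in the documents:

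- r = rate of first relapse among patients still at risk and tested in the SVR24 window;
- g = share of the planned denominator that those patients form.

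If earlier relapsers are not counted again, the planned rate is r × g. With r = 4%:

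- g = 0.9: 3.6%
- g = 0.8: 3.2%
- g = 0.5: 2.0%

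In counts, 6 relapses among 150 tested patients is 4.0% (Wilson 95% CI 1.9–8.5%). The same 6 over a planned denominator of 300 is 2.0% (0.9–4.3%).

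Earlier failures lower g even with full re-testing. Take 417 patients at about 95%: 396 responders and 21 failures, and assume that all 21 had EoT response and completed treatment. Then g = 396/417 = 0.95 with everyone re-tested, and 0.95 × 0.8 = 0.76 with 80% re-tested. A true 2% becomes 1.90% and 1.52%. If none of the 21 qualified for the denominator, g equals the re-tested share.

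**SVR24.** Assumed inputs, apart from the planning rates for p:

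- p = SVR12 rate in CPSFU12;
- f = share of SVR12 responders tested after day 126;
- s = share of SVR12 responders with no late test for safety reasons (condition iii);
- no late relapse, and no SVR12 failure later counted as an SVR24 responder.

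The CPSFU12 failures (1 − p) all stay in CPSFU24. Hence

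SVR24 = p·f / (p·f + p·s + 1 − p).

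| p | s | f = 0.9 | f = 0.8 | f = 0.5 |
|---|---|---|---|---|
| 90% | 0 | 0.81/0.91 = 89.0% | 0.72/0.82 = 87.8% | 0.45/0.55 = 81.8% |
| 95% | 0 | 0.855/0.905 = 94.5% | 0.76/0.81 = 93.8% | 0.475/0.525 = 90.5% |
| 90% | 1% | 0.81/0.919 = 88.1% | 0.72/0.829 = 86.9% | 0.45/0.559 = 80.5% |
| 95% | 1% | 0.855/0.9145 = 93.5% | 0.76/0.8195 = 92.7% | 0.475/0.5345 = 88.9% |

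With s = 0, the f at which the drop is exactly one point is 0.89 × 0.10 / (0.90 × 0.11) = 0.90 for p = 90%, and 0.94 × 0.05 / (0.95 × 0.06) = 0.82 for p = 95%. At f = 1 there is no drop.

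Two strata at 90% and 95%, 5 points apart, would show 87.8% and 93.8% (6.0 points) if f = 0.8 in both, and 81.8% and 90.5% (8.7 points) if f = 0.5.

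**Does SAP 4.2.3 repair this?** No. If the window is empty but "there is an HCV RNA value after the window, then it will be imputed into the EoTR or SVR window respectively". A patient with such a value after the SVR24 window already has a result after day 126 and is in CPSFU24. The rule that a still-missing value is a failure acts only on patients inside the population, and the untested responder is outside it.

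**Against the primary CP SVR12 rate** (missing = failure). Let R be SVR12 responders, F retained failures and M patients lost before day 70. SVR24 is the lower of the two only if f < (F + R·s)/(F + M). With assumed R = 376, F = 21 and M = 21, the CP SVR12 rate is 376/418 = 90.0% and the CPSFU12 rate is 376/397 = 94.7%. SVR24 is 93.5% at f = 0.8 and 90.0% at f = 0.5 (s = 0). The crossover is 21/42 = 0.50 for s = 0 and 24.76/42 = 0.59 for s = 1%.

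**The case against.** The strongest reply is that little harm follows. No objective concerns durability of response, no SVR24-versus-SVR12 comparison is planned, and both endpoints are secondary and descriptive. That stands, and it limits the weight of the point.

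The plan is also open about who is excluded. SAP 4.2.5 says: "The reasons for exclusion from a particular population will be also summarized in the frequency tables". Part of the remedy is therefore already planned. The premature-termination table will not help, since non-completion there means "no HCV RNA assessment performed at least 10 weeks post-treatment", so a responder last tested at day 84 is a completer. The population-exclusion summary should still catch that patient. The table shells in Part II were not available, so whether those counts appear beside the SVR24 rate cannot be checked.

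The size may be small. An SVR24 visit with HCV RNA is on the schedule, and any value after day 126 qualifies for CPSFU24. At p = 97% and f = 0.8 (s = 0) the drop is only 0.7 points (0.776/0.806 = 96.3%). In a stratum with no failures and no safety drop-outs it is zero at any f.

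Three stronger readings are tempting, and the documents do not support them.

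- A reader might infer that the reported relapse24 must be too low. The SAP does not say whether a week-12 relapser still positive in days 127–210 counts again. If so, the numerator rises and the net direction is unknown.
- A reader might infer that SVR24 must fall below the primary SVR12 rate. That order is not fixed, as shown above.
- A reader might take the CPSFU12 SVR12 rate as the true value. CPSFU12 applies the same kind of entry rule at day 70, so it is only a comparator.

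**Conclusion.** The point holds within limits.

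The relapse24 denominator includes patients who could not show a first relapse in that window, because they were not tested or had already failed. Relapse first detected there is understated by the factor g. The documents give no value for g or r.

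SVR24 in CPSFU24 lies below SVR12 in CPSFU12 without late relapse whenever some SVR12 responders are not re-tested and at least one failure or safety drop-out is retained. The direction follows from the entry rule. The size rests on the undocumented re-test share: with s = 0, about 1 point or less when f is at least 0.90 (p = 90%) or 0.82 (p = 95%), and 2.2 or 1.2 points at f = 0.8.

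The primary SVR12 analysis is not affected. This is a worthwhile clarification of secondary descriptive endpoints, not a flaw in the main result.

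**What to change.** Amend SAP 4.2.7.2.1 in two places.

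1. **Relapse24.** Define the denominator as CP patients with EoT response who completed treatment, had no HCV RNA of 50 IU/mL or more and no recorded virologic failure from EoT through day 126, and have an observed HCV RNA value in days 127–210. Apply the 4.2.3 rule for values after day 210 in the same way whatever the result, and keep the 4.2.3 rule on new HCV treatment. Define the numerator as relapse first detected in that window. Report late failures recorded without a value as a separate count or sensitivity analysis. Adding them to the main rate while value-less responders stay out would bring back outcome-dependent entry. For example, if 2 such failures joined the 6 in 150 above, the rate would be 8/152 = 5.3% against an assumed true 4%.

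2. **SVR24.** Beside the CPSFU24 rate, show the number of SVR12 responders excluded for no test after day 126, and the number kept for safety or virologic-failure reasons without a late test. State that a difference from SVR12 is not by itself evidence of lost response.

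Optionally, add the proportion still below 50 IU/mL in the SVR24 window among SVR12 responders, using observed values only for both outcomes. Values carried into the SVR12 window would turn some late relapses into SVR12 failures. Suppose 300 week-12 responders are all tested late, 12 relapse late, and 3 of those 12 are among 75 patients with no day 70–126 test. Carried values give 288/297 = 97.0%; observed values give 216/225 = 96.0%, the assumed truth.

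The cost is SAP wording and a few table rows, with no new data. The downside is a smaller relapse24 denominator and a rate that assumes re-testing is unrelated to late relapse.

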4.1.2 Secondary Parameters

The secondary effectiveness endpoints are:

- The percentage of patients with virological response (HCV RNA <50 IU/mL) at EoT (defined as last intake of ABBVIE REGIMEN or ribavirin)
- The percentage of patients with relapse (defined as HCV RNA <50 IU/mL at EoT followed by HCV RNA ≥50 IU/mL)
- Sustained virological response 24 weeks after EoT (SVR24, i.e. patients with HCV RNA < 50 IU/mL 24 weeks after EoT)
- The number and percentage of patients meeting each and any of the following SVR12 non-response categories:
 - On-treatment virologic failure (breakthrough [defined as above] or failure to suppress [each measured on-treatment HCV RNA value ≥50 IU/mL])
 - Relapse (defined as HCV RNA <50 IU/mL at EoT or at the last on-treatment HCV RNA measurement followed by HCV RNA ≥50 IU/mL post-treatment for subjects who complete treatment [not more than 7 days shortened])
 - Premature study drug discontinuation with no on-treatment virologic failure
 - Missing SVR12 data and/or none of the above criteria

Further secondary variables are:

- Type of treatment regimen (\pm Dasabuvir, \pm RBV, intended and actual combination, dose and duration)
- Adherence
 - Percentage of the DAA dose taken in relation to the target dose of DAA (cumulative dose taken divided by target dose in percent)
 - Percentage of the RBV dose taken in relation to the target dose of RBV (cumulative dose taken divided by target dose in percent)
 - Percentage of missed RBV treatment days in relation to the target number of RBV treatment days
- Co-morbidities and concomitant medication
- Serious and non-serious adverse events and pregnancy occurrences
- PAM-13, BMQ, PSP satisfaction and utilization questionnaires
- Resistant virus variants at post-baseline time points compared to baseline

No data will be imputed for any effectiveness or safety analyses except for the analyses of the HCV RNA endpoints and PRO questionnaires (if applicable). For further details see sections 4.2.3 and 4.2.7.2.3, respectively.

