EoT	Actual EoT	Study day of last dose# (28 days prior to last dose - 7 days post last dose)
Post Treatment	12 weeks (SVR 12 window)	\geq 70-126 days post last dose
	24 weeks (SVR24 window)	127-210 days post last dose

[^]values must also be \leq 7 days post last dose

\geq study day 2

*RVR = rapid virological response

All reported safety laboratory test results will be assigned to one of the time points using the time windows specified in the table below.

Table 4 - Analysis Time Windows for Safety Laboratory Data

Phase	Time point	Time Window
Pre-Treatment	Baseline	Last value prior to start of study treatment (i.e. \leq study day 1)
Treatment Weeks	4 (day 29)	Study day during treatment period (Study day 1 = first treatment day)
	8 (day 57)	15 – 42 [^]
	12 (day 85)	43 – 70 [^]
	16 (day 113)	71 – 98 [^]
EoT	Actual EoT	Study day of last dose# (28 days prior to last dose - 7 days post last dose)
Post Treatment	4 weeks (28 days post last dose)	8– 56 post last dose
	12 weeks (84 days post last dose)	57 – 126 days post last dose
	24 weeks (168 days post last dose)	127 – 252 days post last dose

[^]values must also be \leq 7 days post last dose

\geq study day 2

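### Read literally, SAP 4.2.7.2.1 puts a relapse seen only on days 8–69 after the last dose in the relapse denominator but in neither relapse12 nor relapse24

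*SAP*

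**What the plan says.** SAP 4.1.2 lists as a secondary endpoint: "The percentage of patients with relapse (defined as HCV RNA <50 IU/mL at EoT followed by HCV RNA ≥50 IU/mL". It sets no time limit on the positive value. Protocol 9.7.3.2 defines relapse the same way.

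SAP 4.2.7.2.1 then describes the estimate: "The relapse rates will be estimated stratified by SVR window (i.e. during SVR12 window" is relapse12, and the SVR24 window is relapse24. The denominator is core-population patients with EoT response who completed treatment and either had an HCV RNA measurement at day 70 or later "or was a treatment failure between EoT and 70 days post-treatment".

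SAP Table 3 fixes the windows. EoT is "28 days prior to last dose - 7 days post last dose", SVR12 is "70-126 days post last dose" and SVR24 is "127-210 days post last dose".

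The non-response table in the same section also has a relapse category. It accepts response at EoT or "at the last on-treatment HCV RNA measurement followed by HCV RNA ≥ 50 IU/mL post-treatment and completed treatment as defined previously", again without a window.

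**The concern.** The denominator names early failures explicitly, but the two strata that hold the events start at day 70. A patient whose relapse is found between the EoT window and day 70, and who has no usable positive value afterwards, is at risk with no stratum in which to be an event.

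The plan itself expects such patients:

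- SAP Table 2 marks HCV RNA at the early post-treatment visit, where data are available.
- SAP 4.2.5 treats patients without an HCV RNA test at 10 weeks or later as not completing the study, and lists post-treatment relapse among the reasons.
- SAP 4.2.1 keeps patients in the sufficient-follow-up population on the strength of a last value of 50 IU/mL or more, even without a test at day 70 or later.

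At stake is a named secondary effectiveness rate with its own table and confidence interval. On the literal text any error makes the regimen look better, and the same patient can be a relapse in one output and a non-event in another.

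**Working it through.** **No figure to reproduce.** The documents state no relapse rate, relapse count or precision target for relapse. The check is therefore a reading of the rules, followed by an illustration.

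**Step 1: the uncovered interval.** The EoT window ends on day 7 after the last dose, and the SVR12 window starts on day 70. Days 8 to 69 (69 − 8 + 1 = 62 days) lie in no HCV RNA window.

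**Step 2: who falls in the gap.** The patient must meet all of these conditions:

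- completed treatment and had EoT response;
- had a first positive value on days 8–69, which meets the early-failure criterion for the denominator;
- has no usable positive value on days 70–210.

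The last condition arises in two ways. The patient may not be re-tested, since SAP 4.2.2 leaves testing to the physician. Or the patient may be re-treated, since SAP 4.2.3 excludes values from the start of new HCV treatment. An early relapser who is still positive at a usable test on days 70–210 does fall in a window and is counted.

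**Step 3: do the imputation rules close the gap?** Flanking imputation in SAP 4.2.3 needs undetectable or unquantifiable values on both sides, so it does not apply after a positive value. The other rule moves a value from after a window back into it. No rule carries an early positive value forward.

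**Step 4: size.** Let N be the denominator, R all relapses, and E the early-only relapses of Step 2.

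- Rate counting every relapse after EoT response: R/N.
- Literal rate (relapse12 and relapse24 events together): (R − E)/N = (R/N) × (1 − E/R).

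The relative understatement is E/R. The inputs are assumptions. N = 400 is a round number near the 417 evaluable patients in SAP 3.2, R = 12 (3%) is illustrative, and E/R is unknown. Intervals are 95% Wilson, the SAP's method.

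| E/R | Events counted | Literal rate (95% CI) |
|---|---|---|
| 0% | 12 | 3.00% (1.72–5.17) |
| 25% | 9 | 2.25% (1.19–4.22) |
| 50% | 6 | 1.50% (0.69–3.23) |
| 75% | 3 | 0.75% (0.26–2.18) |

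With R = 4 or R = 20, a 50% share takes 1.00% to 0.50% or 5.00% to 2.50%.

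**Step 5: effect on SVR12.** Under SAP 4.2.3 a patient still without a value in the SVR12 window after imputation is a failure. An early relapser with no later value is thus already an SVR12 non-responder.

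**The case against.** The best defence is that SAP 4.2.3 covers HCV RNA endpoints in general and treats a value still missing from the relevant window as a failure. If relapse12 belongs to the SVR12 window, an early failure with no later value would become a relapse12 event. That would also explain why early failures are named in the denominator. The same section calls re-treated patients failures in summaries of viral response.

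This is a plausible account of the intention, but the text does not say it. The detailed sentences name RVR, EoT response and SVR, not relapse. Applied to relapse24, the rule would turn denominator patients who were negative in the SVR12 window and never tested again into relapses, which cannot be meant. The re-treatment sentence concerns viral response summaries, not relapse.

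Several limits do stand:

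- A reader might infer that every relapse before day 70 is lost. The documents do not support that, because those with a later usable positive value are counted.
- A patient with no value in the EoT window may have the early positive value imputed to EoT. That patient is then not an EoT responder and never enters the denominator.
- The sum of relapse12 and relapse24 is this review's summary, not a stated output.
- A reader might expect the relapse and non-response tables to agree exactly. They need not. The non-response table accepts response at the last on-treatment value and is restricted to SVR12 non-responders, while relapse24 can occur after SVR12.
- The table shells in SAP Part II are not among the documents reviewed and may settle the point.

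**Conclusion.** The mismatch between numerator and denominator is real on the face of SAP 4.2.7.2.1, and it conflicts with the window-free definition in SAP 4.1.2 and Protocol 9.7.3.2. On the literal reading the relapse rate can be too low by the early-only share of relapses. For an assumed 12 in 400, 3.0% falls to 1.5% at a 50% share and does not change at 0%.

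It would go too far to say that the rate is too low. The documents give neither the number of relapses nor the share seen only before day 70, and the sponsor may have meant early failures to count in relapse12. The point concerns one descriptive secondary rate. SVR12 is not affected, and in the non-response table early relapses in completers still appear as relapse.

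**What to change.** In SAP 4.2.7.2.1, define the events directly:

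- **Relapse12:** first HCV RNA of 50 IU/mL or more after EoT response, at any time after the EoT window through day 126. Failures before day 70 then count in relapse12.
- **Relapse24:** first such value on days 127–210, in patients not already relapsed.

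State also what counts as a treatment failure in the early-failure criterion. A row for days 8–69 in SAP Table 3 is optional, because the definition works without it. Do not require the relapse and non-response tables to match exactly. A footnote should explain differences by the latter's wider response definition and its restriction to SVR12 non-responders.

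The cost is SAP wording only, with no new data. The relapse rate may come out less favourable. If early failures were always meant to count in relapse12, the change only records that.
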